Chronic temporomandibular joint (TMJ) disorders (TMD) are the main cause of facial pain, and the second cause of musculoskeletal pain after low-back pain. The cause of TMD is unknown and therapy is usually empirical. Systematic reviews have shown that more research is needed to elucidate the benefits of occlusal adjustment for TMD. The risk factors for chronic unilateral TMD include dental (occlusal) premature contacts and habitual chewing on the affected side; therefore, a new occlusal therapy is proposed to restore physiological jaw closure and chewing function.

Aims

The primary endpoint will be the average change in pain score from baseline to the six-month assessments.

Efficacy will be demonstrated by superior pain relief with the active treatment compared with the placebo.

Methods

Study design

A phase 3, randomized, single (extensible to up three) centre, 6-month parallel-group, patient- and observer-blinded, placebo-controlled clinical trial to assess the efficacy of occlusal adjustment on recovery of physiological jaw closure and chewing function in patients with TMD.

Study population

Inclusion criteria: TMD patients, aged 18-65 years with full dentates and normo-occlusion suffering significant pain (pain scores ≥ 4 and ≤ 9 ; method: visual analogue/numerical rating scale (VAS/NRS); 0 = no pain, 10 = worst imaginable pain). Main exclusion criterion is the requirement of excessive enamel removal to equilibrate the dental articulation (occlusion).

Intervention

Active therapy will consist of the elimination of premature tooth contacts and the reduction of the steeper lateral anterior guidance. *Placebo* therapy will be conducted in a manner identical to the active adjustment, but no enamel will be removed.

Outcomes

Main outcome: self-reported pain intensity on the affected side measured by the VAS and/or NRS scale.

Secondary outcomes: maximum comfortable mouth opening (using a Boley gauge), chewing function (observed on the habitual chewing side) and quality of life using self-administered tests. Time frame: baseline and both 3- and 6-months follow-up.

Sample size estimation

Based on data from a previous study, we assume a standard deviation of 2.4 for this variable. We will test the null hypothesis of no treatment effect at the two-sided 0.05 level. With a fixed sample size design, a total sample size of 88 subjects (extended to 110 for drop-outs) with complete follow-up would provide power of 0.8 to detect changes in pain score of 1.5 units between the active and placebo treatment groups.

Interim analysis plan and stopping rules

The Data and Safety Monitoring Board will be responsible for activating early stopping. The study will employ an interim analysis plan with a single interim analysis after 70% of participants have completed the six-month follow-up visit. Using the Lan-DeMets version of the O'Brien-Fleming stopping rule, the critical value for statistical significance at the interim analysis (under both intention-to-treat and *per-protocol* sets) will be +2.438, corresponding to a nominal two-sided P value of 0.0146.

Statistical analysis plan

For analysis of baseline characteristics, qualitative variables will be expressed as frequencies and percentages (25th -75th percentiles) and continuous variables as means (standard deviation). Fisher's exact or McNemar tests will be used to compare the distributions of binary variables; Student t test or measurements repeated analysis of variance will be used to compare normal variables, and the Wilcoxon or Mann-Whitney U test for non-normally distributed continuous variables.

All analyses will be conducted by two independent statisticians according to the intention-to-treat approach (the primary outcome was also analyzed as per protocol).

The objective of this analysis is to adjust regression models that explain the outcomes of interest as a function of time and group. Based on the properties of the analyzed variables, the model fit of the analyses based on the linear mixed-effects model or the beta mean regression model with mixed effects, using the Akaike Information Criterion or the Bayes Information Criterion. Plots of residuals were used to check that the model assumptions were met and to assess goodness of fit. Statistical significance level was set at 0.05. All the analyses were conducted using the software R (R Development Core Team), including the "lme4" and the "gamlss" packages or IBM SPSS24.

Sponsor

University of Santiago de Compostela, [name]

Funder

Ministry of Science and Innovation of the Government of Spain (Grant nº PI11/02507).

European Development Fund (EDF). Fondo Europeo de Desarrollo Regional (FEDER) . "Una manera de hacer Europa"

Autonomic Committee of the Research Ethics of Galicia: CAEI approval number 2009/017; updated on November 29, 2013).

Date trial started

11th August, 2014.

Expected end date

July, 2017.

The authors state that there are no conflicts of interest to report.

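### Does measuring the main outcome by VAS and/or NRS leave the primary test open to bias or an inflated error rate?

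*Combined protocol and SAP*

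**What the plan says.** The Outcomes section defines the primary variable as follows: "Main outcome: self-reported pain intensity on the affected side measured by the VAS and/or NRS scale". The eligibility criterion in Study population uses the same pair of instruments and gives them one set of anchors: "method: visual analogue/numerical rating scale (VAS/NRS); 0 = no pain, 10 = worst imaginable pain".

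Elsewhere the score is singular and carries no instrument name. Under Aims: "The primary endpoint will be the average change in pain score from baseline to the six-month assessments". In the sample size paragraph: "Based on data from a previous study, we assume a standard deviation of 2.4 for this variable", with 88 completers who "would provide power of 0.8 to detect changes in pain score of 1.5 units between the active and placebo treatment groups". The test is also singular: "We will test the null hypothesis of no treatment effect at the two-sided 0.05 level".

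The visit schedule is "Time frame: baseline and both 3- and 6-months follow-up". Nothing in the document says which scale is primary, whether a patient must stay on one scale, or what happens if both are recorded.

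**The concern.** The trial has one primary endpoint, and its measuring instrument is left open. The wording can be read in three ways, and each seems to carry a risk.

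- **One scale or the other, fixed within a patient.** The analysis pools two instruments, although the sample size assumes one standard deviation.
- **One scale or the other, with changes between visits.** A patient scored on one scale at baseline and the other at six months has a change score that includes the difference between instruments.
- **Both scales in every patient.** Two primary comparisons could each be tested at 0.05, with no rule for which one decides.

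A biased treatment difference or two chances of a positive result would weaken the trial's only confirmatory claim.

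**Working it through.** **Inputs.** From the sample size paragraph: difference 1.5, standard deviation 2.4, two-sided alpha 0.05, power 0.80, 88 completers, 110 with drop-outs. Allocation is not stated; 1:1 (44 per arm) is assumed. The documents give no correlation between the scales, no offset between them and no switching rate, so all of these are assumptions shown as ranges.

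**1. The plan's sample size.** Per arm, n = 2(1.960 + 0.842)² × (2.4/1.5)² = 40.2, so 41 per arm and 82 in total. The t-test needs 41.17, so 42 per arm and 84 in total. Dividing 41.17 by the Mann-Whitney efficiency 3/π = 0.955 gives 43.1, so 44 per arm and 88 in total, which matches the plan. The plan does not say which test was used for sizing. Drop-outs: 88/0.80 = 110, also a match.

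**2. Power at 44 per arm with one instrument.** The standard error is 2.4 × √(2/44) = 0.512, and 1.5/0.512 = 2.93. Power = Φ(2.93 − 1.96) = 0.834. The t-test gives 0.826.

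**3. One scale per patient.** A constant offset between scales is present at baseline and at six months, so it cancels in that patient's change. No bias arises from it.

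**4. Switching between visits: bias.** Bias in the treatment difference = offset × (share switching in one arm − share switching in the other).

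| Assumed offset (points) | Arm difference 0% | 10% | 30% |
|---|---|---|---|
| 0.25 | 0 | 0.025 | 0.075 |
| 0.5 | 0 | 0.05 | 0.15 |
| 1.0 | 0 | 0.10 | 0.30 |

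The largest entry is 0.30/1.5 = 20% of the target difference. It needs a full point between two scales with the same end points and a 30% imbalance in switching between blinded, randomised arms.

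**5. Switching between visits: noise.** If a share p switches equally in both arms, independently of response, the standard deviation becomes √(2.4² + offset² × p(1 − p)).

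- Offset 0.5, p = 0.5: √(5.76 + 0.0625) = 2.413; power at 88 is 0.830.
- Offset 1.0, p = 0.5: √(5.76 + 0.25) = 2.452; power at 88 is 0.819 by the normal approximation and 0.810 by the t-test.
- If the final test were Mann-Whitney, the effective size per arm is 44 × 0.955 = 42.0. The t-test power formula at that size falls from 0.808 to 0.791 in the 1.0-point case.

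The loss is between 0.015 and 0.017 in the worst case shown, whichever test is used.

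**6. Both scales tested, either may win.** The false-positive rate is P(|Z₁| > 1.96 or |Z₂| > 1.96) for a bivariate normal with correlation ρ.

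| ρ (assumed) | Rate |
|---|---|
| 0 | 1 − 0.95² = 0.0975 |
| 0.80 | 0.078 |
| 0.90 | 0.070 |
| 0.95 | 0.065 |
| 0.99 | 0.057 |

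Both scores are self-reports of the same pain on the same side with the same anchors, so the lower rows are the relevant ones. The calculation applies only if the plan lets either scale decide, and no section says so.

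**The case for a change.** The strongest case for a change is that the primary variable of a confirmatory trial should be fixed in writing, and that doing so is cheap: naming one scale leaves alpha at 0.05 and the sample at 88 (110). Shared anchors make the two scores look interchangeable but do not say which one counts. The same open choice exists at the interim look. Even at a correlation of 0.99, an either-may-win analysis exceeds 0.05. Extension to three centres gives some room for inconsistent use.

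Part of this stands. The text is ambiguous, no other section resolves it, and naming the instrument would be tidier. But each harm depends on a step the plan does not take. The error inflation needs a two-test procedure, whereas the plan describes one endpoint and one null hypothesis; the absence of a selection rule is not itself a rule that either result may be claimed. The bias needs switching that differs by arm. The noise, where it can be bounded, is small.

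The cheapness is also less clear than it looks. The trial started in August 2014 with an expected end in July 2017, and the statistical analysis plan section partly uses the past tense. If scores have already been recorded, a single instrument cannot be imposed afterwards on patients who do not have it.

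**Conclusion.** The instrument is left unspecified, but the plan as written leads to no demonstrated wrong result, and no change is called for. A competent analyst would take one 0 to 10 pain score per patient, on the same scale at each visit, and run the one comparison the plan describes. That reading keeps alpha at 0.05 and leaves the 88 (110) untouched.

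The sizes behind this are:

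- no between-arm bias when switching is equal across arms;
- a power loss of at most about 0.017 for a constant offset of up to 1 point, which leaves power above 0.80 by the normal approximation or t-test and at 0.791 if a rank test is used;
- an error rate of 0.057 to 0.078 only under an either-may-win rule that is not in the plan.

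These rest on assumed correlations, offsets and switching shares, on 1:1 allocation, and on randomisation and blinding working as described. The noise bound covers a constant offset only. A trial report that presented two primary pain results and claimed success on the better one would be a different matter, but it would depart from this plan.

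### The interim boundary pairs z = 2.438 with P = 0.0146, but z = 2.438 is a two-sided P of 0.0148

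*Combined protocol and SAP*

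**What the plan says.** The section on the interim analysis plan and stopping rules makes the Data and Safety Monitoring Board responsible for activating early stopping. It plans "a single interim analysis after 70% of participants have completed the six-month follow-up visit". The boundary is derived "Using the Lan-DeMets version of the O'Brien-Fleming stopping rule", and the critical value at the look "will be +2.438, corresponding to a nominal two-sided P value of 0.0146".

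The overall level comes from the sample size section: "We will test the null hypothesis of no treatment effect at the two-sided 0.05 level". That section also gives the planned numbers, "a total sample size of 88 subjects (extended to 110 for drop-outs) with complete follow-up". The P value of 0.0146 appears nowhere else, so no other part of the document confirms or corrects it.

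**The concern.** The sentence presents z and P as two forms of one threshold, so each should convert to the other under the standard normal distribution. They do not. An interim z between 2.438 and 2.442 crosses the boundary as a critical value and misses it as a P value, and the plan does not say which form governs if they disagree. A stopping threshold should have one value, fixed before the interim data are seen.

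Little is at stake in practice. The gap is in the fourth decimal of P, and the stated P is on the strict side.

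**Working it through.** **Inputs, all from the document.** Critical value 2.438; nominal two-sided P 0.0146; one look at 70%; Lan-DeMets version of O'Brien-Fleming; overall two-sided level 0.05; SD 2.4; effect 1.5; 88 complete subjects, or 110 with the allowance for drop-outs.

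**1. The plan's critical value is reproduced.** With 0.025 per side, the O'Brien-Fleming-type function spends, over both sides,

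2 × [2 − 2Φ(z₀.₉₈₇₅ / √t)], where z₀.₉₈₇₅ = 2.2414.

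At t = 0.70: 2.2414/√0.70 = 2.6790, with upper tail 0.003692. The amount spent is 4 × 0.003692 = 0.01477. At a first look, the amount spent is the nominal P, so z = Φ⁻¹(1 − 0.01477/2) = 2.4380. This agrees with the stated 2.438.

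**2. The plan's P value is not reproduced.**
- From z to P: 2 × [1 − Φ(2.438)] = 2 × 0.007384 = 0.01477, or 0.0148.
- From P to z: Φ⁻¹(1 − 0.0146/2) = Φ⁻¹(0.9927) = 2.4422.

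**3. Other explanations tried.**
- *Third-decimal rounding.* Any z that rounds to 2.438 (2.4375 to 2.4385) gives P from 0.01479 to 0.01475. A P that rounds to 0.0146 needs z from 2.4409 to 2.4434. The ranges do not overlap.
- *Timing of the look.* P rounds to 0.0146 only for t from 0.6974 to 0.6986. That is 61.37 to 61.48 of 88, or 76.71 to 76.84 of 110, and neither range contains a whole number. With 110 subjects, 70% is exactly 77, which returns 2.438 and 0.0148.
- *A t reference distribution.* P for 2.438 rises to 0.0177 with 60 df and 0.0171 with 75 df, further from 0.0146.
- *Other boundaries.* Classic O'Brien-Fleming at 0.70 gives 2.400 and 0.0164. Applying the spending function once to the two-sided 0.05 gives 2.343 and 0.0191. Neither is the stated pair.

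**4. Size of the discrepancy.**
- Null probability of falling between the thresholds: 0.01477 − 0.0146 = 0.00017.
- Overall two-sided error (bivariate normal, correlation √0.70). The document gives no final critical value, so two are assumed:

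| Assumed final value | Interim z = 2.438 | Interim z = 2.442 |
|---|---|---|
| 2.000 | 0.04999 | 0.04991 |
| 1.96 | 0.05414 | 0.05407 |

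- Difference needed at the look, assuming 62 complete subjects in equal arms: SE = 2.4 × √(4/62) = 0.6096. Then 2.438 × 0.6096 = 1.486 points and 2.4422 × 0.6096 = 1.489 points.
- Chance of crossing under the plan's own effect: the full-information mean of z is 1.5 / (2.4 × √(2/44)) = 2.932. At t = 0.70 it is 2.932 × √0.70 = 2.453. The probability of exceeding the boundary is 0.506 with 2.438 and 0.504 with 2.442.

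**The case against.** Four points can be made for leaving the sentence alone.

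- **The operative rule is arguably clear.** The critical value is the subject of the sentence and the P value is only a gloss on it. Since 2.438 is correct for the named method, the plan states the right boundary. This reading is reasonable and is one reason the point is minor. But a board that works from a reported P value would apply 0.0146, and the plan does not say that z takes precedence.
- **Coarser rounding could produce the figure.** Cutting z to 2.44 gives an upper tail of 0.00734. Rounded to 0.0073 and doubled, that is 0.0146. This is a plausible route, though the document does not say how P was obtained. It explains the slip without making the pair consistent: unrounded, z = 2.44 gives 0.0147, and z = 2.438 gives 0.0148.
- **The denominator of the 70% is not fixed.** Totals other than 88 and 110 do give P = 0.0146, for example 60/86, 67/96 or 74/106. This is right, so the whole-number argument holds only for the two totals that the plan names. At those other fractions, however, z is about 2.442 to 2.443, so the stated pair still fails.
- **The effect is negligible and conservative.** This is also right. It limits the severity but does not make the stated equivalence true.

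**Conclusion.** The point holds, as a minor correction. The stated P value is wrong for the stated critical value: 0.0148, not 0.0146. The critical value is the one to keep, because it follows from the plan's own method, information fraction and overall level. This conclusion needs only the normal distribution and the inputs given in the plan.

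The consequences are very small: a disagreement probability of about 0.0002 under the null, a change in overall error below 0.0001, 0.003 pain points in the difference needed, and 50.6% versus 50.4% for the chance of crossing under the planned effect. The overall error figures rest on assumed final critical values, and the pain difference on 62 complete subjects in equal arms. The finding itself depends on neither. No sample size, safety provision or trial conclusion turns on it.

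**What to change.** Replace 0.0146 by 0.0148 in the stopping rule. Add that if the look falls at an information fraction other than 0.70, z and P will be recomputed together from the spending function. For example, 61 of 88 gives 2.452 and 0.0142, and 62 of 88 gives 2.429 and 0.0152. The cost is one corrected figure and one sentence, with no added patients, data or redesign.

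### The plan sets an interim efficacy boundary but no final one; a final test at 0.05 gives overall alpha of about 0.054, and the interim P value is misprinted

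*Combined protocol and SAP*

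**What the plan says.** Under 'Interim analysis plan and stopping rules' the plan schedules "a single interim analysis after 70% of participants have completed the six-month follow-up visit". The boundary is set "Using the Lan-DeMets version of the O'Brien-Fleming stopping rule", and the interim critical value, applied to both the intention-to-treat and per-protocol sets, is +2.438, "corresponding to a nominal two-sided P value of 0.0146". The section ends there, with no boundary or nominal level for the final analysis.

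Two other statements give a level. The sample size text says: "We will test the null hypothesis of no treatment effect at the two-sided 0.05 level". The statistical analysis plan says: "Statistical significance level was set at 0.05". Neither mentions the alpha already spent at the interim.

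The sample size is "a total sample size of 88 subjects (extended to 110 for drop-outs) with complete follow-up", so two counts could serve as the base for the 70%. The plan does not say which applies.

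**The concern.** A look at which the trial can stop for efficacy uses up part of the 5% error. The final test must then be slightly stricter than 1.96 if the total is to stay at 5%. The plan spends at the interim and does not say that the final test pays for it. A final P between 0.0455 and 0.05 would be significant under the level printed in the analysis plan and not significant under the named stopping rule. That dispute would concern the primary conclusion and would arise after the data are known.

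The interim rule also carries two thresholds that do not match, a Z of 2.438 and a P of 0.0146. Finally, 2.438 belongs to 70% of the information, so the monitoring board needs a trigger that can be counted without interpretation. With 2.438 held fixed, a look later than 70% is conservative and a look earlier than 70% is more lenient than the named rule.

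**Working it through.** **Inputs, all from the plan:** two-sided alpha 0.05; one interim look at t = 0.70; interim critical value 2.438 with stated P 0.0146; 88 completers, 110 with drop-outs; difference 1.5; standard deviation 2.4.

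**1. Reproduce the interim critical value.** The O'Brien-Fleming-type spending function, with two-sided 0.05 taken as twice one-sided 0.025, is α(t) = 4 × [1 − Φ(z/√t)], where z = 2.2414 is the upper 0.0125 point.
- At t = 0.70, z/√t = 2.2414/0.8367 = 2.679, so α(0.70) = 0.01477.
- The two-sided Z for 0.01477 is 2.438. The plan's critical value reproduces.

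**2. Check the P value paired with it.**
- 2 × [1 − Φ(2.438)] = 0.01477, or 0.0148.
- Any Z that rounds to 2.438 gives 0.01475 to 0.01479, so rounding does not explain 0.0146.
- P = 0.0146 needs Z = 2.442, or t = 0.698.
- Other routes fail too. A t distribution with 60 to 108 degrees of freedom gives 0.0164 to 0.0177. The classic O'Brien-Fleming boundary gives Z = 2.400, P = 0.0164. Spending 0.05 as if one-sided gives Z = 2.343, P = 0.0191.

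**3. Overall type I error.** Under the null, the interim and final Z are bivariate normal with correlation √0.70 = 0.837. Overall alpha = 1 − P(|Z₁| < 2.438 and |Z₂| < c).

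| Final critical value c | Final nominal P | Overall two-sided alpha |
|---|---|---|
| 1.960 | 0.0500 | 0.0541 |
| 2.000 | 0.0455 | 0.0500 |

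Solving for exactly 0.05 gives c = 1.9999. A simulation with 4,000,000 draws gives 0.0542 and 0.0501 for the two rows.

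**4. Effect of the denominator.** 70% of 88 is 61.6, about 62; 70% of 110 is 77. With 2.438 kept at the interim:

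| Look and final count | t | Alpha with final 1.96 | Final value that holds 0.05 |
|---|---|---|---|
| 62 of 88 | 0.705 | 0.0541 | 1.999 |
| 77 of 88 | 0.875 | 0.0510 | 1.969 |
| about 62 of 110 | 0.56 | 0.0565 | 2.024 |

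If 77 have completed and the final count is 88, the named rule would itself give an interim Z of 2.130, well below 2.438. If the look and the final analysis use the same base (62 of 88, or 77 of 110), t is about 0.70 either way. This is therefore an ambiguity, not a contradiction.

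**5. Cost in power.** At 88 completers the drift is (1.5/2.4) × √88/2 = 0.625 × 4.690 = 2.932. By normal approximation, fixed-design power at 1.96 is 0.834. With 2.438 then 2.000 it is 0.829, a loss of about 0.5 percentage points, and still above the stated 0.8.

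**The case against.** The plan never says that the final test uses 1.96. It names a Lan-DeMets rule and an overall two-sided 0.05, and with one look at 70% those two facts determine a final value of 2.000. The sentence setting significance at 0.05 follows the text on models and residuals, and could be read as a general or overall level. This stands to the extent that 0.054 is conditional on reading the final test at 0.05. It does not remove the gap, because the plan neither prints the final value nor says it will be derived, and the level in the analysis plan carries no qualification.

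Other readings of the interim rule give less inflation:
- If the plus sign means that only the upper boundary counts, alpha with a final 1.96 is 0.0521.
- If both analysis sets must cross, less is spent at the interim. The plan gives no correlation between the two analyses. Assuming 0.98, 0.95 or 0.90 gives 0.0530, 0.0525 or 0.0520 by simulation.
- Both readings together give 0.0511 to 0.0516 over the same correlations.

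These figures are fair, and 0.054 is not the only value the text supports. All of them remain above 0.05.

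The P value slip is minor. The printed 0.0146 is the stricter threshold, so using it cannot raise the error rate. The chance that Z falls between 2.438 and 2.442 at 62 completers is 0.0002 under the null and 0.0017 at a difference of 1.5. Alone it is a typographical correction, and the undefined denominator alone is only missing detail.

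**Conclusion.** The concern holds. The main fault is the missing final boundary. Read as written, with a two-sided interim at 2.438, 70% information and a final test at 1.96, overall alpha is 0.0541 instead of 0.05, an excess of about 0.4 percentage points. The other readings considered run from 0.0510 to 0.0565, all above 0.05 when the final test uses 1.96. The printed interim P of 0.0146 is wrong for 2.438 and should be 0.0148; this would rarely change a decision. The base of the 70% is undefined, which matters because 2.438 is the named rule's value only at 70% information. The results assume approximately normal test statistics with independent increments. The plan should be corrected, but neither its size nor its design is in question.

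**What to change.** In the SAP and the monitoring board's charter:
- Correct the nominal two-sided P for 2.438 to 0.0148.
- Define the trigger as a count that falls at 70% of the planned information, for example 62 of the 88 planned completers with six-month primary outcome data.
- State that the interim and final boundaries are computed from the spending function at the information fraction observed, with planning values of 2.438 (P = 0.0148) at the interim and 2.000 (P = 0.0455) at the final analysis of the primary outcome.

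The cost is one corrected figure and two sentences, with no change in sample size. The downside is a final threshold for the primary outcome slightly stricter than 0.05, at about 0.5 percentage points of power relative to the fixed design.

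### The models are described only in terms of time and group; adding baseline pain would usually tighten the six-month comparison, and costs about 1% of variance if the slope is near 1

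*Combined protocol and SAP*

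**What the plan says.** Under Aims the endpoint is defined as follows: "The primary endpoint will be the average change in pain score from baseline to the six-month assessments". Under Study population, patients enter "suffering significant pain (pain scores ≥ 4 and ≤ 9" on a 0 to 10 scale, so a baseline pain value exists for everyone eligible. The visit schedule under Outcomes reads: "Time frame: baseline and both 3- and 6-months follow-up".

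The sample size section states: "Based on data from a previous study, we assume a standard deviation of 2.4 for this variable". It sizes the trial at 88 completers (110 with drop-outs) to "detect changes in pain score of 1.5 units between the active and placebo treatment groups" at two-sided 0.05 with power 0.8.

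The Statistical analysis plan gives the model terms in one sentence: "The objective of this analysis is to adjust regression models that explain the outcomes of interest as a function of time and group". The candidate families are a "linear mixed-effects model or the beta mean regression model with mixed effects, using the Akaike Information Criterion or the Bayes Information Criterion". Nothing in the document enters baseline pain as a covariate or states that baseline means are held equal across arms. Nothing rules out either approach.

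**The concern.** A mixed model with baseline as one of the visits, terms for time, group and their interaction, and free baseline means in each arm has a six-month time-by-group contrast equal to the difference in mean change. The plan's wording therefore leads most naturally to an unadjusted change-score comparison.

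That comparison fixes the coefficient of baseline pain at 1. If the true slope of six-month on baseline pain is lower, the change score carries baseline variation that a model estimating the slope would remove. Large-sample theory says the adjusted comparison is never less precise. At this sample size it pays only a small price for estimating one extra coefficient.

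What is at stake is precision, not validity. There is also a reason to settle the matter in writing: if baseline adjustment is left open, a choice between adjusted and unadjusted results could be made after the data are seen, which would undermine the primary test.

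**Working it through.** **Inputs from the documents.** Difference 1.5; SD 2.4, read here as the SD of change; two-sided alpha 0.05; 88 completers; entry pain 4 to 9.

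**Assumptions.** 1:1 allocation (44 per arm), because the ratio is not stated. Baseline SD s0 of 1.2 to 1.44, where 1.44 is a uniform spread over 4 to 9 (5/√12). Slope b of six-month on baseline pain from 0.3 to 1. The documents give no baseline SD, slope or correlation.

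**The plan's own figure.** The normal formula gives 2 × (1.960 + 0.842)² × 5.76 / 2.25 = 40.2, so 41 per arm and 82 in total. The t test needs 42 per arm, 84 in total. The stated 88 is thus slightly generous. With 44 per arm the noncentral t gives power 0.826 on 86 df and a 95% half-width of 1.02. The inflation to 110 is 88/0.8. The small gap between 84 and 88 does not affect this point.

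**Variance of the two comparisons.** Per patient,

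- change: 2.4² = 5.76
- baseline-adjusted, before the cost of estimating b: 5.76 − (1 − b)² × s0²
- baseline-adjusted, net: the line above × 85/84 (a factor of 1.012), with 85 df

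Example, s0 = 1.44 and b = 0.5: 5.76 − 0.25 × 2.0736 = 5.242; × 85/84 = 5.304; 5.304/5.76 = 0.921, a net saving of 7.9%.

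| s0 | b | implied correlation | raw saving | net saving | power | half-width |
|---|---|---|---|---|---|---|
| 1.2 | 0.3 | 0.16 | 12.2% | 11.2% | 0.868 | 0.96 |
| 1.2 | 0.5 | 0.25 | 6.2% | 5.1% | 0.845 | 0.99 |
| 1.2 | 0.7 | 0.33 | 2.2% | 1.1% | 0.830 | 1.01 |
| 1.2 | 1.0 | 0.45 | 0 | −1.2% | 0.822 | 1.02 |
| 1.44 | 0.3 | 0.19 | 17.6% | 16.7% | 0.888 | 0.93 |
| 1.44 | 0.5 | 0.30 | 9.0% | 7.9% | 0.855 | 0.98 |
| 1.44 | 0.7 | 0.39 | 3.2% | 2.1% | 0.834 | 1.01 |
| 1.44 | 1.0 | 0.51 | 0 | −1.2% | 0.822 | 1.02 |

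**Break-even.** |1 − b| = √(5.76/85)/s0, which is 0.217 at s0 = 1.2 and 0.181 at s0 = 1.44. Adjustment gains when the slope is below about 0.78 to 0.82 or above about 1.18 to 1.22.

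**Simulation.** With 40,000 trials per case at s0 = 1.44, the ratio of adjusted to change-score variance was 0.830, 0.915, 0.996 and 1.012 at slopes 0.3, 0.5, 0.8 and 1.0. Theory gives 0.833, 0.921, 0.997 and 1.012. Both estimators averaged −1.50, so neither is biased.

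**If 2.4 is the SD of the six-month score instead.** Change variance is 5.76 + s0²(1 − 2b); adjusted variance is (5.76 − b² s0²) × 85/84. At slopes 0.3 to 0.5, power is 0.77 to 0.83 for change and 0.83 to 0.855 adjusted. At slope 1 it is 0.917 to 0.952 for change and 0.914 to 0.950 adjusted. On this reading the unadjusted comparison can fall below the planned 0.8.

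**The case against.** The strongest reply is that the plan contains no error here. The change-score contrast is unbiased, matches the stated endpoint and exceeds 0.8 power if 2.4 is the SD of change. That is correct, and it is why this is a recommendation about efficiency.

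The size of the gain also rests on quantities that the documents do not supply. The 17% figure is the most favourable case tabulated. The entry range restricts baseline spread; with s0 = 1.0 the net saving is only 3.2% at slope 0.5 and 0.4% at slope 0.7, with a 0.5% loss at slope 0.8. So even the sign of the effect cannot be settled from the documents. This stands, but the imbalance between gain and loss remains: the worst case costs about 1.2% of variance and 0.004 of power.

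A mixed model with a common baseline mean is also a function of time and group, so the statisticians may already intend one. In that case most of the gain is already there. The plan does not say so, and a sentence would settle it.

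Finally, the figures compare a six-month change score with a baseline-adjusted six-month comparison in completers. They are not the precision of the full longitudinal model with drop-outs, and they do not carry over to the beta model. Both limits stand.

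**Conclusion.** The concern holds as a matter of precision and pre-specification; nothing here suggests bias or a wrong estimand. With 44 per arm, a linear model and 2.4 as the SD of change, adjusting for baseline pain saves 5% to 17% of variance at slopes 0.3 to 0.5, is close to neutral around slope 0.8, and loses 1.2% at slope 1. The 5% to 17% saving is equivalent to roughly 5 to 18 extra completers (88/0.949 ≈ 93; 88/0.833 ≈ 106). The amount actually gained depends on an unknown slope and on an assumed baseline SD of 1.2 to 1.44; a narrower spread would shrink it. Confidence is medium for that reason. The change is worth making because the downside is small and known, and the covariate is already collected.

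**What to change.** State in the Statistical analysis plan that the linear mixed model for pain at 3 and 6 months includes baseline pain, group, visit, group-by-visit and baseline-by-visit. Alternatively, keep baseline as a response with its mean constrained to be equal across arms. Name the six-month group difference as the primary contrast; this clarifies the stated endpoint and does not alter it. The unadjusted change can stay as a supporting analysis.

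If the beta mixed model is used, enter baseline pain there too, and note that its adjusted coefficient is not on the 1.5-point scale.

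The cost is SAP wording, provided that it is fixed before unblinded data are seen, including at the planned interim analysis. Statistically it uses one degree of freedom for the six-month comparison and about 1% of variance if the slope is near 1. It needs no new data, patients or software, since lme4 and gamlss are already planned.
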